#### **Pembrolizumab:**

Dose increase or decrease of pembrolizumab will not be permitted in individual subjects. If a dose of pembrolizumab is withheld for toxicity, then subjects may resume dosing, if appropriate, at their next scheduled appointment or when toxicity has improved as described in [Table 6](#) below.

AEs (both nonserious and serious) observed may occur shortly after the first dose through several months after the last dose of treatment. Pembrolizumab must be withheld for drug-related toxicities and severe or life-threatening AEs as per [Table 6](#) below. See Section 5.6 – Rescue Medications & Supportive Care for supportive care guidelines, including use of corticosteroids.

In addition, subjects should receive appropriate supportive care measures as deemed necessary by the treating investigator. Suggested supportive care measures, as described in Section 5.6.1 – Supportive Care Guidelines, are also included in [Table 6](#).

AEs associated with pembrolizumab exposure may represent an immunologic etiology. These immune-related AEs (irAEs) may occur shortly after the first dose through several months after the last dose of treatment and may affect more than one body system simultaneously. Therefore, early recognition and initiation of treatment is critical to reduce complications. Based on existing clinical trial data, most irAEs were reversible and could be managed with interruptions of pembrolizumab, administration of corticosteroids and/or other supportive care. For suspected irAEs, ensure adequate evaluation to confirm etiology or exclude other causes. Additional procedures or tests such as bronchoscopy, endoscopy, or skin biopsy may be included as part of the evaluation. Based on the severity of irAEs, withhold or permanently discontinue pembrolizumab and administer corticosteroids. Dose modification and toxicity management guidelines for irAEs associated with pembrolizumab are provided in [Table 6](#).

Table 6 Dose Modification and Toxicity Management Guidelines for Immune-related AEs Associated with Pembrolizumab or Previously-Administrated Ipilimumab

Immune-related AEs	Toxicity Grade or Conditions (CTCAEv4.0)	Action Taken to Pembrolizumab	irAE Management with Corticosteroid and/or Other Therapies	Monitor and Follow-up
Pneumonitis	Grade 2	Withhold	
 
Administer corticosteroids (initial dose of 1-2 mg/kg prednisone or equivalent) followed by taper
 
	
 
Monitor subjects for signs and symptoms of pneumonitis
 
Evaluate subjects with suspected pneumonitis with radiographic imaging and initiate corticosteroid treatment
 
Add prophylactic antibiotics for opportunistic infections
 

	Grade 3 or 4, or recurrent Grade 2	Permanently discontinue		
Diarrhea/colitis	Grade 2 or 3	Withhold	
 
Administer corticosteroids (initial dose of 1-2 mg/kg prednisone or equivalent) followed by taper
 
	
 
Monitor subjects for signs and symptoms of enterocolitis (i.e. diarrhea, abdominal pain, blood or mucus in stool with or without fever) and of bowel perforation (i.e. peritoneal signs and ileus).
 
Subjects with <math>\geq</math> Grade 2 diarrhea suspecting colitis should consider GI consultation and performing endoscopy to rule out colitis.
 
Subjects with diarrhea/colitis should be advised to drink liberal quantities of clear fluids. If sufficient oral fluid intake is not feasible, fluid and electrolytes should be substituted via IV infusion.
 

	Grade 4	Permanently discontinue		
AST/ALT elevation or Increased Bilirubin	Grade 2	Withhold	
 
Administer corticosteroids (initial dose of 0.5- 1 mg/kg prednisone or equivalent) followed by taper
 
	
 
Monitor with liver function tests (consider weekly or more frequently) until liver enzyme value returned to baseline or is stable
 

	Grade 3 or 4	Permanently discontinue	
 
Administer corticosteroids (initial dose of 1-2 mg/kg prednisone or equivalent) followed by taper
 
	

Immune-related AEs	Toxicity Grade or Conditions (CTCAEv4.0)	Action Taken to Pembrolizumab	irAE Management with Corticosteroid and/or Other Therapies	Monitor and Follow-up
Type 1 diabetes mellitus (T1DM) or Hyperglycemia	Newly onset T1DM or Grade 3 or 4 hyperglycemia associated with evidence of $\beta$ -cell failure	Withhold	
 
Initiate insulin replacement therapy for subjects with T1DM
 
Administer antihyperglycemic in subjects with hyperglycemia
 
	
 
Monitor subjects for hyperglycemia or other signs and symptoms of diabetes
 

Hypophysitis	Grade 2	Withhold	
 
Administer corticosteroids and initiate hormonal replacements as clinically indicated
 
	
 
Monitor for signs and symptoms of hypophysitis (including hypopituitarism and adrenal insufficiency)
 

	Grade 3 or 4	Withhold or permanently discontinue a		
Hyperthyroidism	Grade 2	Continue	
 
Treat with nonselective beta-blockers (e.g. propranolol) or thionamides as appropriate
 
	
 
Monitor for signs and symptoms of thyroid disorders
 

	Grade 3 or 4	Withhold or permanently discontinue a		
Hypothyroidism	Grade 2-4	Continue	
 
Initiate thyroid replacement hormones (e.g. levothyroxine or liothyronine) per standard of care
 
	
 
Monitor for signs and symptoms of thyroid disorders.
 

Nephritis and renal dysfunction	Grade 2	Withhold	
 
Administer corticosteroids (prednisone 1-2 mg/kg or equivalent) followed by taper
 
	
 
Monitor changes of renal function
 

	Grade 3 or 4	Permanently discontinue		
Myocarditis	Grade 1 or 2	Withhold	
 
Based on severity of AE administer corticosteroids
 
	
 
Ensure adequate evaluation to confirm etiology and/or exclude other causes
 

	Grade 3 or 4	Permanently discontinue		

Immune-related AEs	Toxicity Grade or Conditions (CTCAEv4.0)	Action Taken to Pembrolizumab	irAE Management with Corticosteroid and/or Other Therapies	Monitor and Follow-up
All Other immune-related AEs	Intolerable/ persistent Grade 2	Withhold	
 
Based on type and severity of AE administer corticosteroids
 
	
 
Ensure adequate evaluation to confirm etiology or exclude other causes
 

	Grade 3	Withhold or discontinue based on the type of event. Events that require discontinuation include but not limited to: Guillain-Barre Syndrome, encephalitis, Stevens-Johnson Syndrome and toxic epidermal necrolysis		
	Grade 4 or recurrent Grade 3	Permanently discontinue		

a Withhold or permanently discontinue pembrolizumab is at the discretion of the investigator or treating physician.
 
Note: For subjects with Grade 3 or 4 immune-related endocrinopathy where withholding of pembrolizumab is required, pembrolizumab may be resumed when AE resolves to ≤ Grade 2 and is controlled with hormonal replacement therapy or achieved metabolic control (in case of T1DM).
 
General Instructions:
 
 
Corticosteroid taper should be initiated upon AE improving to ≤ Grade 1 and continue to taper over at least 4 weeks.
 
For situations where pembrolizumab has been withheld, pembrolizumab can be resumed after AE has been reduced to Grade 1 or 0 and corticosteroid has been tapered. Pembrolizumab should be permanently discontinued if AE does not resolve within 12 weeks of last dose or corticosteroids cannot be reduced to ≤10 mg prednisone or equivalent per day within 12 weeks.
 
For severe and life-threatening irAEs, IV corticosteroid should be initiated first followed by oral steroid. Other immunosuppressive treatment should be initiated if irAEs cannot be controlled by corticosteroids.
 
 
Abbreviations: AEs=adverse events; ALT (SGPT)=alanine aminotransferase (serum glutamic pyruvic transaminase); AST (SGOT)=aspartate aminotransferase (serum glutamic oxaloacetic transaminase); CTCAE=Common Terminology Criteria for Adverse Events; DKA=diabetic ketoacidosis; GI = gastrointestinal; IV=intravenous; irAE=immune-related adverse events; T1DM=Type 1 diabetes mellitus
				

Pembrolizumab may cause severe or life threatening infusion-reactions including severe hypersensitivity or anaphylaxis. Signs and symptoms usually develop during or shortly after drug infusion and generally resolve completely within 24 hours of completion of infusion. Dose modification and toxicity management guidelines on pembrolizumab associated infusion reaction are provided in [Table 7](#).

Table 7 Pembrolizumab Infusion Reaction Dose Modification and Treatment Guidelines

NCI CTCAE Grade	Treatment	Premedication at Subsequent Dosing

Grade 1  Mild reaction; infusion interruption not indicated; intervention not indicated
	
Increase monitoring of vital signs as medically indicated until the subject is deemed medically stable in the opinion of the investigator.
	
None

Grade 2  Requires therapy or infusion interruption but responds promptly to symptomatic treatment (e.g., antihistamines, NSAIDs, narcotics, IV fluids); prophylactic medications indicated for ≤24 hours
	
Stop Infusion.  Additional appropriate medical therapy may include but is not limited to:  IV fluids  Antihistamines  NSAIDs  Acetaminophen  Narcotics  Increase monitoring of vital signs as medically indicated until the subject is deemed medically stable in the opinion of the investigator.  If symptoms resolve within 1 hour of stopping drug infusion, the infusion may be restarted at 50% of the original infusion rate (e.g. from 100 mL/hr to 50 mL/hr); otherwise dosing will be withheld until symptoms resolve and the subject should be premedicated for the next scheduled dose.  Subjects who develop Grade 2 toxicity despite adequate premedication should be permanently discontinued from further treatment with pembrolizumab.
	
Subject may be premedicated 1.5 h (± 30 minutes) prior to infusion of pembrolizumab with:  Diphenhydramine 50 mg po (or equivalent dose of antihistamine).  Acetaminophen 500-1000 mg po (or equivalent dose of analgesic).

NCI CTCAE Grade	Treatment	Premedication at Subsequent Dosing

Grades 3 or 4            Grade 3:            Prolonged (i.e., not rapidly responsive to symptomatic medication and/or brief interruption of infusion); recurrence of symptoms following initial improvement; hospitalization indicated for other clinical sequelae (e.g., renal impairment, pulmonary infiltrates)            Grade 4:            Life-threatening; pressor or ventilatory support indicated
	
Stop Infusion.            Additional appropriate medical therapy may include but is not limited to:            Epinephrine**            IV fluids            Antihistamines            NSAIDs            Acetaminophen            Narcotics            Oxygen            Pressors            Corticosteroids            Increase monitoring of vital signs as medically indicated until the subject is deemed medically stable in the opinion of the investigator.            Hospitalization may be indicated.            **In cases of anaphylaxis, epinephrine should be used immediately.  Subject is permanently discontinued from further treatment with pembrolizumab.
	
No subsequent dosing

Appropriate resuscitation equipment should be available at the bedside and a physician readily available during the period of drug administration.            For further information, please refer to the Common Terminology Criteria for Adverse Events v4.0 (CTCAE) at http://ctep.cancer.gov
		

Abbreviations: CTCAE=Common Terminology Criteria for Adverse Events; IV=intravenous; NCI=National Cancer Institute; NSAIDs=nonsteroidal anti-inflammatory drugs; PO=oral.

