	† Results in or prolongs an existing inpatient hospitalization (hospitalization is defined as an inpatient admission, regardless of length of stay, even if the hospitalization is a precautionary measure for continued observation. (Note: Hospitalization for an elective procedure to treat a pre-existing condition that has not worsened is not a serious adverse event. A pre-existing condition is a clinical condition that is diagnosed prior to the use of a Merck product and is documented in the patient's medical history.); or	
	† Is a congenital anomaly/birth defect (in offspring of subject taking the product regardless of time to diagnosis); or	
	Is a new cancer (that is not a condition of the study) (although not serious per ICH definition, is reportable to the Sponsor within 24 hours to meet certain local requirements); or	
	Is an overdose (whether accidental or intentional). Any adverse event associated with an overdose is considered a serious adverse event for collection purposes. An overdose that is not associated with an adverse event is considered a non-serious event of clinical interest and must be reported within 24 hours.	
	Other important medical events that may not result in death, not be life threatening, or not require hospitalization may be considered a serious adverse event when, based upon appropriate medical judgment, the event may jeopardize the subject and may require medical or surgical intervention to prevent one of the outcomes listed previously (designated above by a †).	
Duration	Record the start and stop dates of the adverse event. If less than 1 day, indicate the appropriate length of time and units	
Action taken	Did the adverse event cause the Sponsor's product to be discontinued?	

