	Rechallenge	Was the subject re-exposed to the Sponsor's product in this study? If yes, did the AE recur or worsen? If yes, this is a positive rechallenge. If no, this is a negative rechallenge. (Note: This criterion is not applicable if: (1) the initial AE resulted in death or permanent disability, or (2) the trial is a single-dose drug trial); or (3) Sponsor's product(s) is/are used only one time). NOTE: IF A RECHALLENGE IS PLANNED FOR AN ADVERSE EVENT WHICH WAS SERIOUS AND WHICH MAY HAVE BEEN CAUSED BY THE SPONSOR'S PRODUCT, OR IF REEXPOSURE TO THE SPONSOR'S PRODUCT POSES ADDITIONAL POTENTIAL SIGNIFICANT RISK TO THE SUBJECT, THEN THE RECHALLENGE MUST BE APPROVED IN ADVANCE BY THE SPONSOR CLINICAL DIRECTOR AS PER DOSE MODIFICATION GUIDELINES IN THE PROTOCOL.
	Consistency with Trial Treatment Profile	Is the clinical/pathological presentation of the AE consistent with previous knowledge regarding the Sponsor's product or drug class pharmacology or toxicology?
The assessment of relationship will be reported on the case report forms /worksheets by an investigator who is a qualified physician according to his/her best clinical judgment, including consideration of the above elements.		
Record one of the following	Use the following scale of criteria as guidance (not all criteria must be present to be indicative of a Sponsor's product relationship).	
Yes, there is a reasonable possibility of Sponsor's product relationship.	There is evidence of exposure to the Sponsor's product. The temporal sequence of the AE onset relative to the administration of the Sponsor's product is reasonable. The AE is more likely explained by the Sponsor's product than by another cause.	
No, there is not a reasonable possibility of Sponsor's product relationship	Subject did not receive the Sponsor's product OR temporal sequence of the AE onset relative to administration of the Sponsor's product is not reasonable OR the AE is more likely explained by another cause than the Sponsor's product. (Also entered for a subject with overdose without an associated AE.)	

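### Table 6 withholds pembrolizumab for myocarditis from Grade 1, but its general resumption rule has no myocarditis threshold and permits re-dosing with Grade 1 still present

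*Combined protocol and SAP*

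**What the plan says.** Section 5.2.1.2 of the protocol directs that pembrolizumab be withheld for drug-related toxicity according to Table 6. After a withheld dose, "subjects may resume dosing, if appropriate, at their next scheduled appointment or when toxicity has improved as described in" Table 6.

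The myocarditis row of Table 6 has two tiers: withhold at Grade 1 or 2, and permanently discontinue at Grade 3 or 4. Its steroid entry is "Based on severity of AE administer corticosteroids", so no fixed dose or grade for starting steroids is set.

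The General Instructions under the table apply to every row:

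- Instruction 1: "Corticosteroid taper should be initiated upon AE improving to ≤ Grade 1 and continue to taper over at least 4 weeks".
- Instruction 2, for any withheld case: "pembrolizumab can be resumed after AE has been reduced to Grade 1 or 0 and corticosteroid has been tapered". It then sets an outer limit: "Pembrolizumab should be permanently discontinued if AE does not resolve within 12 weeks of last dose", or if steroids cannot be brought down to 10 mg prednisone equivalent a day in the same time.

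The only type-specific resumption rule in the table is the Note on Grade 3 or 4 endocrinopathy. There is none for myocarditis.

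Table 10 in Section 7.2.4 adds a rechallenge rule. Advance approval by the Sponsor's clinical director is needed if the event was serious and may have been caused by the product, or if re-exposure "POSES ADDITIONAL POTENTIAL SIGNIFICANT RISK TO THE SUBJECT, THEN THE RECHALLENGE MUST BE APPROVED IN ADVANCE". A hospital admission makes an event serious "even if the hospitalization is a precautionary measure for continued observation".

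**The concern.** Myocarditis is the one category in which the highest grade that allows resumption is also a grade at which the row withholds. A subject whose Grade 2 myocarditis has improved to Grade 1 and whose steroids have been tapered meets the resumption rule, although a subject first seen with Grade 1 myocarditis would have the dose held.

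Two sites could both follow Table 6 and manage the same subject differently. One waits for full resolution; the other re-doses with low-grade myocarditis still present. For a non-serious event, no fixed rule decides between them.

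The table is still in use. After Amendment 06, subjects continue on open-label pembrolizumab, some may receive up to 17 further doses in the Second Course Phase, and the title of Table 6 also covers events attributed to ipilimumab given earlier. Section 7.2.7 states that no further data monitoring committee reviews will take place, so the site-level rule carries more of the weight. What is at stake is subject safety and consistent handling across sites, not an efficacy estimate.

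**Working it through.** The plan gives no figure to reproduce. The check sets the parts of Table 6 side by side.

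**Step 1. Lowest grade at which each row withholds (or may withhold).**

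| Category | Lowest withhold grade |
|---|---|
| Pneumonitis | 2 |
| Diarrhea/colitis | 2 |
| AST/ALT or bilirubin | 2 |
| Type 1 diabetes or hyperglycemia | New-onset diabetes (ungraded), or Grade 3 hyperglycemia with beta-cell failure |
| Hypophysitis | 2 |
| Hyperthyroidism | 3 |
| Hypothyroidism | None (continue) |
| Nephritis | 2 |
| Myocarditis | 1 |
| All other | 2, if intolerable or persistent |

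Myocarditis is 1 of 10.

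**Step 2. Margin between withholding and resuming under Instruction 2.** Margin = lowest withhold grade − highest resume grade, and Instruction 2 sets the highest resume grade at 1. For pneumonitis, colitis, liver, hypophysitis, nephritis and the residual category the margin is 2 − 1 = 1 grade. For myocarditis it is 1 − 1 = 0.

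**Step 3. Read the myocarditis row as an onset trigger only, with Instruction 2 alone governing resumption.** This is the reading kindest to the plan. Take each onset grade in turn.

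- *Onset at Grade 2.* The event falls to Grade 1 and steroids, if given, are tapered. The resumption condition is met. Re-dosing is permitted with Grade 1 myocarditis present.
- *Onset at Grade 1, taking Grade 1 as sufficient.* The grade condition is met when the event is found. If no steroid is given there is no taper to wait for, so Instruction 2 adds nothing to the hold.
- *Onset at Grade 1, taking the wording to require a fall in grade.* The event must reach Grade 0. The milder event then faces a stricter test than the Grade 2 event.

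Neither way of handling a Grade 1 onset gives a sensible rule alongside the Grade 2 case.

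**Step 4. How soon can a Grade 2 event be re-dosed?** With steroids, and assuming the taper must be finished, the earliest point is 4 weeks × 7 = 28 days after reaching Grade 1, longer than one 21-day cycle. That meaning is an assumption. Instruction 2 also uses 10 mg a day as a threshold, and if reaching that dose counted as tapered, resumption could come earlier, with no minimum stated. Without steroids, Table 6 adds no further wait and the body text allows the next scheduled appointment where appropriate.

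**Step 5. Do the other provisions settle it?**

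- The body text requires judgment and improvement. Grade 2 to Grade 1 is an improvement, and the sentence refers back to Table 6.
- The 12-week limit depends on resolution, which is not defined as Grade 0.
- Table 10 applies to serious events. For a non-serious event only its additional-risk limb remains. That limb is a matter of judgment, and it too refers back to the protocol's dose-modification guidelines.

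**The case against.** The strongest answer is that the row and the instruction do different jobs. The row says when to withhold; Instruction 2 begins once a dose has been withheld and is the only Table 6 text that says when to restart. The table itself supports this. Hypophysitis is withheld at Grade 2, yet the Note says that after a Grade 3 or 4 event "pembrolizumab may be resumed when AE resolves to ≤ Grade 2 and is controlled with hormonal replacement therapy". A grade named in a row is therefore not always a continuing bar to dosing.

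That stands. A reader might infer that Table 6 contradicts itself, with the row forbidding at Grade 1 what the instruction allows. The documents do not support that reading, because no row states a resumption rule. Step 3 therefore adopts the onset reading, and the incoherence remains. The hypophysitis comparison also has a limit: there the overlap comes from a deliberate, type-specific Note tied to hormone replacement, whereas for myocarditis it comes from a general rule that does not mention the event.

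Second, resumption is permissive and hedged. Investigator judgment, the steroid taper, the row's requirement for adequate evaluation, the 12-week limit, the discontinuation criteria in Section 5.8.1 and Table 10 all apply. Table 10 also counts other important medical events as serious, which could bring in myocarditis managed without admission. This stands as mitigation. It narrows the gap to non-serious events but supplies no threshold for them.

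Third, nothing in the documents shows that Grade 0 is better than Grade 1 as a threshold. That is correct. Grade 0 is a cautious choice consistent with withholding from Grade 1; the Sponsor could choose another threshold, but should state one.

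**Conclusion.** The point holds as a gap in a safety rule. Table 6 withholds for myocarditis from Grade 1 but has no myocarditis-specific resumption threshold, and the general threshold gives either an empty Grade 1 hold or a stricter test for the milder event. It affects 1 of 10 categories, and mainly non-serious Grade 1 or 2 events.

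Two stronger inferences are not supported. A reader might conclude that the protocol tells sites to re-dose subjects with active myocarditis; it only permits this, subject to judgment, steroid taper and, for serious or higher-risk events, advance Sponsor approval. A reader might also conclude that subjects were harmed or that trial results are in doubt; the documents give no myocarditis counts, and no endpoint, event count, power or alpha depends on this rule. Randomization has closed and ipilimumab has stopped, so few future cases may be in scope.

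The conclusion rests on the wording of Table 6 alone. The 28-day figure assumes that tapered means the taper is complete. This is a cheap improvement, not a defect that threatens the trial.

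**What to change.** Add one line to the myocarditis row, or as an exception to General Instruction 2: *Resume only after resolution to Grade 0 and completion of any corticosteroid taper; otherwise permanently discontinue.* Keep the 12-week limit and Table 10 unchanged, and leave the endocrinopathy Note as it is. The new line also settles what resolution means for myocarditis when the 12-week limit is applied.

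The cost is the line itself, a letter to sites, and some missed treatment. With the last dose at week 0, doses due at weeks 3, 6 and 9 may be held before the limit decides at week 12, so at most 3 doses on the 3-week schedule. The added loss is smaller where steroids are used, because a taper of at least 28 days already spans at least one scheduled dose. A subject whose Grade 1 event persists past 12 weeks would stop permanently. No new scheduled test is needed: Section 7.1.2.4 already provides for further ECGs when clinically indicated.
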